Probiotics are defined as live microbial organisms that when administered in sufficient amounts, can provide a protective benefit to the host (Hojsak, 2017). Use of probiotics in a pediatric population exposed to antibiotics and gastrointestinal surgery such as an appendectomy may provide a protective effect and prevent ADD (Alper, Zangwill, LaRue & Manheimer, 2017; Hayes & Vargas, 2016). In a meta-analysis of randomized controlled trials in pediatrics, literature found that treatment with *Lactobacillus rhamnosus GG* (LGG) reduced in risk of ADD from 23% to 9.6% (RR, 0.48; 95% Cl, 0.26 to 0.89) (Szajewska & Kolodziej, 2015). Studies indicate it is suggested to administer LGG simultaneously with the initiation of antibiotic therapy, before the modification of gut microbiota and overgrowth of pathogens (Szajewska & Kolodziej, 2015).

Lactobacillus rhanmosus GG(LGG®)(Culturelle) is an over the counter dietary supplement that can help to restore the balance in the gut by promoting colonization to support better digestion and immune health. As such, this dietary supplement is not reviewed and approved by the FDA. This study does not intend to investigate route of administration, dose, patient population, or other factor that significantly increases the risk (or decreases the acceptability of the risk) associated with the use of the dietary supplement.

At Children's Medical Center, we see over 1000 cases of appendicitis a year with approximately 1/3 of those patients being complicated appendicitis. Our current treatment at Children's Medical Center for

complicated appendicitis follows two pathways: 1) drainage and deferred appendectomy approximately 6 to 8 weeks later or 2) immediate appendectomy. All children are typically admitted to the hospital for 3 to 5 days, receive a course of IV antibiotics while in hospital and are discharged with oral antibiotics to complete their treatment. There has been an increase in the number of patients receiving prescribed probiotics after surgery.

We propose to perform a randomized controlled trial where one group of patients receive probiotic therapy and another group of patients does not.

We hypothesize patients given probiotics after a diagnosis of complicated appendicitis with immediate appendectomy who receive antibiotic treatment during their inpatient stay will decrease the overall length of stay (LOS) by 25% vs the LOS in those patients who do not receive probiotics.

3. Concise Summary of Project:

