Those who are in agreeance will be consented for the study following all IRB procedures. Randomization will be used to allocate patients into treatment and control group. The treatment group includes 120 patients who have immediate appendectomy and will receive probiotics. The control group includes 120 patients who have an immediate appendectomy and will receive a placebo. Patients in the treatment group will receive a standard dose of Lactobacillus rhamnosus GG capsule twice a day until discharge. The control group will receive a placebo until discharge. If the patient is unable to swallow the probiotic capsule or placebo, the capsule can be opened and sprinkled with food. Current antibiotic standard of care for complicated appendicitis patients includes: ceftriaxone RTA 50mg/kg dose every 24 hours x 7 days and metronidazole RTA 30mg/kg dose every 24 hours x7 days. In patients with a sensitivity to ceftriaxone, metronidazole RTA 30mg/kg dose every 24 hours x7 days and ciprofloxacin 10-15 mg/kg every 8 hours x 7 days will be administered.

Treating medical team and patients/family will be blinded to whether patient is on probiotic or placebo.

[figure not shown]
Data will be collected as stated in section titled, "Concise Summary of Project."

5. Criteria for Inclusion of Subjects:

- Patients with a post-operative diagnosis of complicated appendicitis who undergo an immediate appendectomy.
- Patients between the ages of 4 and 18 years of age.

6. Criteria for Exclusion of Subjects:

- Patients diagnosed with a complicated appendicitis with deferred appendectomy or nonperforated appendicitis
- Patients that have a history of being immunosuppressed, on immunosuppression therapy, or long-term steroid therapy within the last month.
- Patients that have central line access.
- Patients under 4 years of age.
- Patients that are developmentally delayed and cannot ambulate at baseline. •
- Patients with significant past medical history.
- Patients that are in Child Protective Services custody. •
- Patients that are incarcerated.
- Patients that are pregnant. •
- Patients that speak languages other than English and Spanish.

Study Procedures

7. Sources of Research Material:

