All participants will be patients under the care of the General Surgery Department. Information from the Children's Medical Center EHR will be reviewed. Data on outcomes such as length of stay, presence or absence of diarrhea, ambulation/activity level, abdominal pain, surgical history, medications, emergency department visits, readmission rates and stool counts will be extracted from medical records. Standard demographic data will also be obtained.

8. Recruitment Methods and Consenting Process:

After confirmed complicated appendicitis diagnosis, patients and families will be approached by the study team to participate in the study. If families agree to participate, written consent will be obtained, and the patient will be randomized to a study group.

9. Potential Risks:

Inadvertent disclosure of personal medical information. Special precautions are mentioned below in the paragraph *Procedures to Maintain Confidentiality*.

There are potential risks for patients taking probiotics. There have been reported accounts of sepsis in immunosuppressed patients receiving probiotics. Our study will exclude patients with a history of being immunosuppressed, on immunosuppression therapy, or long-term steroid therapy within the last month.

There is a potential risk of psychological stress. Some of the questions we will ask may make the patient/legal guardians feel uncomfortable.

10. Subject Safety and Data Monitoring:

All data will be stored on a password protected computer approved by UTSW and CMC. Access to study data will be restricted to authorized study personnel only.

All data will be stored on a password protected computer in a RedCap system approved by UTSW and CMC. Access to study data will be restricted to authorized study personnel only.

The Principal Investigators and faculty sponsor will review all patient outcomes on a monthly basis. All adverse events, expected and unexpected will be reviewed within 24 hours by the study team and reported to the DSMB and the IRB as per policy.

11. Procedures to Maintain Confidentiality:

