All patient information and case report forms will be kept in a locked office with limited access. All computer files will be password protected, encrypted and stored on a secure server. Access will be limited to study team members only. Data will be collected and stored in a secured CMC server in RedCap. The case report includes a unique subject number. The data will be collected, analyzed, and archived following strict confidentiality guidelines. The Investigator will consider all information, results, discoveries, records accumulated, records acquired, or deductions in the course of the study as confidential; other than that information to be disclosed by law.

12. Potential Benefits:

There may be benefit to those patients who receive a probiotic during their course of treatment in a reduction of the incidence of AAD. Future patients may benefit if the protocol proven to be effective in decreasing the incidence of AAD.

13. Sample size calculation

Based on the patient population in Children's Medical Center Dallas, the mean and standard deviation of LOS is 114 and 75.6 hours, respectively. The LOS in the probiotic group is expected to be 75% of the control group. With 120 patients in each group, we have 83% of power to detect statistically significant difference in LOS between the probiotic group and control group.

14. Biostatistics

Descriptive analyses of the continuous and categorical data were performed using means, confidence intervals, proportions and frequencies. Wilcoxon Rank Sum test will be used to compare the LOS, as well as the number of diarrheas, between the treatment group and control group. To investigate which type of patients benefits the most from the treatment, regression analysis will be used to model log-transformed LOS. The independent variable will be treatment type and prognostic factors. The statistical analyses were performed with SAS 9.4.

References:

- Alper, B. S., Zangwill, M., LaRue, J., & Manheimer, E. W. (2017). Point of care application of: 'Probiotics for the prevention of pediatric antibiotic-associated diarrhea' (Cochrane review). *European Journal of Integrative Medicine, 12*: 129-130. https://doi.org/10.1016/j.eujim.2017.06.001

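### The log-LOS regression is meant to show which patients benefit most, but no treatment-by-factor term is listed, so as listed it cannot test that

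*Combined protocol and SAP*

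**What the plan says.** Section 14 (Biostatistics) plans a Wilcoxon rank sum test of LOS and of the number of diarrheas between the two groups. It then adds a regression with its own purpose: "To investigate which type of patients benefits the most from the treatment, regression analysis will be used to model log-transformed LOS". The terms are given in the next sentence: "The independent variable will be treatment type and prognostic factors". The prognostic factors are not named, and no model equation is given.

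No treatment-by-factor term, subgroup analysis, stratified model or test of heterogeneity appears elsewhere in the protocol. Section 13 powers only the overall comparison, on the premise that "The LOS in the probiotic group is expected to be 75% of the control group". Baseline data for a subgroup question would be available: Section 7 says "Standard demographic data will also be obtained", and Section 5 admits "Patients between the ages of 4 and 18 years of age".

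**The concern.** Asking which patients benefit most is asking about effect modification. A model with treatment and prognostic factors as main effects has one treatment coefficient and no parameter through which benefit could differ. The factor coefficients show who stays longer, not who gains more from the probiotic, and a reader could take one for the other.

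Two things are at stake. If the listed model is followed, the question is left untested. If factors and interactions are added later, they may be chosen after outcomes are known. Section 10 says "The Principal Investigators and faculty sponsor will review all patient outcomes on a monthly basis", and the blinding statement in Section 4 covers only the treating team and the patients and families. The document does not say whether the monthly review is by arm, so this is a reason to fix the choices early. It is not evidence of unblinding.

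**Working it through.** **Inputs from Section 13.** Mean LOS 114 h, SD 75.6 h, expected ratio 0.75, 120 patients per arm, stated power 83%. Alpha is not stated; two-sided 0.05 is assumed throughout.

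**The plan's own figure.** The difference is 0.25 × 114 = 28.5 h. The standardised value is 28.5 / (75.6 × √(2/120)) = 2.92, and power is Φ(2.92 − 1.96) = 83%. The figure reproduces. It concerns the overall comparison and does not depend on the regression.

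**What the listed model estimates.** log(LOS) = b0 + b1 × treatment + b2 × factors. The LOS ratio is exp(b1) for every patient, whatever the factors are.

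**What it can still rank.** With a common ratio, hours saved grow with expected LOS. Taking the 3 to 5 day stay in the Background (stated there for complicated appendicitis under both treatment pathways), a ratio of 0.75 gives 0.25 × 72 = 18 h saved at 72 h and 0.25 × 120 = 30 h at 120 h. That ordering follows entirely from expected LOS and the constant ratio, which the model assumes and cannot check.

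**Masking (illustrative contrast, not from the document).** With true ratios of 0.60 and 0.90 in two equal halves, the fitted common ratio is exp(0.5 × ln 0.60 + 0.5 × ln 0.90) = √0.54 = 0.735. Simulation gave 0.736.

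**What an interaction term could detect.** Assume lognormal LOS, so log-SD = √ln(1 + (SD/mean)²).
- Control: 75.6/114 gives 0.604.
- Probiotic: also 0.604 if the SD scales with the mean, or 0.760 if the SD stays at 75.6 h around a mean of 0.75 × 114 = 85.5 h.

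For a binary factor with prevalence p (assumed 20% to 50%), the SE of the log ratio of ratios is √[(s0² + s1²)/120 × (1/p + 1/(1−p))]. The target is a ratio of ratios of 0.75, |ln 0.75| = 0.288, an interaction as large as the planned overall effect.

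| Log-SDs (control, probiotic) | p | SE | Power | Power if factors explain 20% of log variance |
|---|---|---|---|---|
| 0.604, 0.604 | 0.2 | 0.195 | 31% | 38% |
| 0.604, 0.604 | 0.5 | 0.156 | 45% | 54% |
| 0.604, 0.760 | 0.2 | 0.2215 | 25% | 31% |
| 0.604, 0.760 | 0.5 | 0.177 | 37% | 44% |

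The last column multiplies the SE by √0.8; the 20% is an assumption. Simulation (4000 trials of 240 patients per setting, no variance explained) gave 32.4%, 46.3%, 23.9% and 37.4% for the four rows, with 4.7–5.4% rejection under the null.

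**Multiplicity.** Two independent tests at 0.05 carry 1 − 0.95² = 9.75% chance of at least one false positive; three carry 1 − 0.95³ = 14.3%.

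**The case against.** The strongest reply is that Section 14 lists variables and does not write out a model. An interaction is built from those same variables, and the stated purpose could be read as implying one. It is true that the text does not exclude interactions, and the conclusion here is limited to the model as listed. But if interactions are implied, neither the factors nor the terms are fixed, and the remedy is the same.

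A second reply is that the plan says it will investigate, not test, and does not define benefit on the ratio scale, so a ranking by hours saved would be an answer. It would be one, but the constant-ratio assumption supplies it and the data do not.

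Third, this is a supplementary regression, and the repaired version would have low power. Both points stand. They limit the severity and are the reason for an exploratory label.

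Fourth, the power figures are for a binary factor, while age is the obvious candidate and is continuous. That also stands. If age were uniform over 4 to 18 (an assumption), power for a ratio of ratios of 0.75 would be about 16–19% when that contrast spans 14 years and about 47–57% when it spans 7. The binary figures are illustrations, and the main conclusion does not rest on them.

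**Conclusion.** The concern holds. As listed, the log-LOS regression estimates a single common LOS ratio, so the plan's question about who benefits most goes untested. That follows from the form of the model and needs no numerical assumption. The illustrations do: the 0.60/0.90 contrast is invented, and the 25–45% power range assumes lognormal LOS, two-sided 0.05, 120 per arm and a binary factor with prevalence 20–50%. The overall Wilcoxon comparisons and the 83% power stand. The point should be fixed, but it does not threaten the main comparison.

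**What to change.** Amend Section 14 before any outcome is seen by arm:

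1. Name a short list of factors recorded before randomisation and already in the planned data, for example age and one other standard demographic.
2. Fit log(LOS) on treatment, those factors and each treatment-by-factor term.
3. Report the LOS ratio with 95% CI by subgroup (for age, at stated ages) and every interaction test. State the number of tests and label the results exploratory.
4. Keep the model without interactions only for the overall adjusted LOS ratio.

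The cost is a few sentences and a few model terms, with no new patients or data. The downside is imprecision: power will be low, each added factor raises the chance of a false positive, and the report should say that a non-significant interaction does not show equal benefit.
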